6.3.3 Treatment patterns

During follow-up, treatment patterns will be characterized in terms of dose, treatment duration, frequency of drug discontinuation, switching and use of add-on therapies. All patients included in the study will be deemed exposed (at least one inebilizumab treatment), but only those with complete 12-month follow-up will be considered in the evaluation of the treatment patterns as described below.

According to the product specifications, the 12-month follow-up will cover 3 potential inebilizumab administrations: initial intravenous (IV) infusion followed by a second

infusion 2 weeks later and a subsequent infusion 6 months after the first treatment (Figure 2A). The first and third infusion will be considered in defining inebilizumab treatment patterns.

Treatment duration will be the sum of days under inebilizumab exposure during the follow-up. Number of days under exposure will be calculated for the first and the third infusion as the difference between end date of inebilizumab exposure period and the administration/prescription/dispensation date (Figure 2B).

[figure not shown]
Inebilizumab complete **exposure period** will be assumed to last 180 days after drug administration/prescription/dispensation. The **end date of the exposure** period will be defined as the end of each inebilizumab exposure period within follow-up or the end date of follow-up if comes first (Figure 2B).

A patient will be considered to be in inebilizumab **continuous use** if no gap longer than 60 days occurs between the end date of the first inebilizumab exposure period and the beginning of the third (2B). **Temporary discontinuation** (intermittent users) will be defined in patients with gaps between inebilizumab exposure periods longer than 60 days but with a subsequent inebilizumab administration/prescription/dispensation during the follow-up. A patient will be defined as having **permanently discontinued** inebilizumab if no subsequent inebilizumab treatment is registered during the follow-up after the end date of the first inebilizumab exposure period.

Switchers will be a subgroup of patients who discontinue inebilizumab (temporarily or permanently) during the follow-up and have other NMOSD maintenance drug administered/ prescribed (Table 9) after the end date of inebilizumab exposure period (2C). The alternative NMOSD drugs will be described.

The use of **add-on therapies** will be identified by administration/prescription/dispensation of other NMOSD maintenance or other immunosuppressive drug(s) (Table 9 and Table 10) during any of inebilizumab exposure period (2D). Corticosteroid pre-medication before inebilizumab infusion (used to reduce potential infusion reactions) will not be considered as an add-on therapy.

Figure 2 Inebilizumab treatment patterns

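### Treatment duration in section 6.3.3 counts days twice when the maintenance infusion is recorded before day 180

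*Protocol*

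**What the plan says.** All of the relevant rules are in Protocol section 6.3.3.

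- Duration is a sum: "Treatment duration will be the sum of days under inebilizumab exposure during the follow-up".
- Two infusions count: "The first and third infusion will be considered in defining inebilizumab treatment patterns". The week-2 infusion is left out.
- The days are "calculated for the first and the third infusion as the difference between end date of inebilizumab exposure period" and the date of the record. This is done once for each of the two infusions.
- Each period "will be assumed to last 180 days after drug administration/prescription/dispensation".
- The end date is the "end of each inebilizumab exposure period within follow-up or the end date of follow-up if comes first".
- The schedule is an initial infusion, an "infusion 2 weeks later and a subsequent infusion 6 months after the first treatment".
- The analysis set is restricted: "only those with complete 12-month follow-up will be considered in the evaluation of the treatment patterns".

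Section 6.3.3 also cites Figure 2B for the exposure days and the end date. The figure is not reproduced in the text available for this review.

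**The concern.** The end-date rule has two arms: the end of that period's own 180 days, and the end of follow-up. The next counted infusion is not among them. Two periods that overlap in calendar time are therefore each counted in full, and the overlap enters the sum twice.

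Maintenance at six calendar months falls only 1 to 4 days after the first 180-day period ends, so a record that is a few days early is enough to create an overlap. Duration of treatment is the first item listed under objective 2 in section 5. The error goes one way only: it overstates exposed time in patients with early maintenance and gives all of them the same value of 360 days.

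**Working it through.** **Inputs.** From section 6.3.3: period length 180 days; first and third infusion counted; truncation only at the end of follow-up; complete 12-month follow-up. Assumed: F = 365 days of follow-up (360 and 366 were also checked). The day d of the maintenance record, counted from the index date, is varied because the protocol gives no distribution or window for it. The protocol states no duration figure, so there is none to reproduce.

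**Formulas.**

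- Duration as written: min(180, F) + [min(d + 180, F) − d].
- Distinct days covered: the size of the union of days 0–180 and d to min(d + 180, F). This equals min(d, 180) + [min(d + 180, F) − d].
- Counted twice: the difference, max(0, 180 − d).

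**Results, F = 365.**

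| d | As written | Distinct days | Counted twice | Excess |
|---|---|---|---|---|
| 120 | 360 | 300 | 60 | 20.0% |
| 150 | 360 | 330 | 30 | 9.1% |
| 160 | 360 | 340 | 20 | 5.9% |
| 170 | 360 | 350 | 10 | 2.9% |
| 175 | 360 | 355 | 5 | 1.4% |
| 179 | 360 | 359 | 1 | 0.3% |
| 180 | 360 | 360 | 0 | 0 |
| 182 | 360 | 360 | 0 | 0 |
| 184 | 360 | 360 | 0 | 0 |
| 200 | 345 | 345 | 0 | 0 |
| 240 | 305 | 305 | 0 | 0 |

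For d below 180 the end of follow-up never cuts the second period, because d + 180 is below 360. The written rule therefore gives 180 + 180 = 360 whatever d is. The overlaps are the same with F = 360 or 366.

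**Nominal schedule.** Counting six calendar months from the first day of each month of 2023 gives 181 to 184 days. Maintenance given exactly on that schedule is unaffected.

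**Average over a cohort: illustration only.** Assume whole-day maintenance dates, normally distributed and clipped to days 120–240.

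| Assumed centre | Assumed SD | Share with d < 180 | Mean overcount, all patients |
|---|---|---|---|
| 182 | 7 | 36% | 1.9 days |
| 182 | 14 | 43% | 4.6 days |
| 182 | 28 | 46% | 10.1 days |
| 190 | 7 | 7% | 0.2 days |
| 190 | 14 | 23% | 2.0 days |

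The share moves from 7% to 46% with the assumed centre and spread. The mean overcount stays between 0.2 and about 10 days, or 0.1% to 3% of the roughly 340 to 357 days covered on average.

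**The case against.** **Figure 2B may show a cut.** It is cited for this very calculation and could not be read here, so the defect is shown for the text only. That limit stands. But the text states the end-date rule in full and would need the clause even if the figure is right.

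**Overlap handling belongs in the SAP.** Section 6.7.1 does leave full variable definitions to the SAP. A missing detail would be no finding. Here, however, the protocol fixes the formula, and the formula gives a wrong total when applied as written. One can argue that days under exposure naturally means calendar days counted once, but the next sentence prescribes two separate differences.

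**360 days is also what carrying unused days forward would give.** If the second 180 days started when the first ended, the total for d below 180 would again be 360. Section 6.3.3 does not say this: each period runs 180 days after its own record.

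**The consequences can be overstated.** This part largely stands.

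- A reader might infer that the defect stops duration from exceeding 360 days. The union of two 180-day periods has the same ceiling.
- A reader might infer that early maintenance becomes invisible. Section 6.7.2.2 separately reports the days between the first and each later treatment. Corrected duration would not separate early from late either: d = 170 covers 350 days, and d = 195 covers 180 + 170 = 350.
- A reader might expect more overlap where exposure is dated by prescription or dispensation. Section 6.9 warns of bias in such sources, but the index date is set in the same way, so a constant lead time cancels in d. Only a lead that differs between the first and the maintenance record would change the overlap, and the protocol does not say that it does.

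**Conclusion.** The point holds for the text of section 6.3.3. A maintenance record at day d below 180 adds 180 − d days twice and sets duration to 360. From day 180 on, the written rule and the count of distinct days agree.

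The per-patient arithmetic needs only the stated rules and a follow-up of about 365 days. How many patients are affected cannot be known from the protocol. A reader might be tempted to state that 36% to 46% of patients are overcounted, but that range follows from centring an assumed normal distribution two days above the threshold; a centre at day 190 with an SD of 7 days gives 7%. A mean effect of a few days is the most that can be said, and that too is a judgement.

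The double count is confined to the duration summary. Continuous use and temporary discontinuation depend on gaps, switching and add-on use depend on dates, and the AESI estimates do not use summed duration. This is a minor defect, worth correcting before the duration variable is programmed.

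**What to change.** In section 6.3.3, define treatment duration as the number of distinct follow-up days covered by at least one counted exposure period. Equivalently, for this calculation, end the first period at the earliest of 180 days, the third (maintenance) infusion record, or the end of follow-up.

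The clause must name the third infusion. A cut at the next inebilizumab record of any kind would end the first period at the week-2 infusion, around day 14, so the text should say that this infusion does not end it.

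Check that Figure 2B shows the same rule and carry it into the SAP. The cost is one clause and, if needed, a redrawn figure. No new data are required, and results for patients with d of 180 or later do not change.

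### A drug recorded only in the tolerated gap of up to 60 days before the third infusion counts as neither add-on nor switch, although the patient is classed as a continuous user

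*Protocol*

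**What the plan says.** All the rules are in protocol section 6.3.3.

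- **Infusions that count.** "The first and third infusion will be considered in defining inebilizumab treatment patterns". The week-2 infusion opens no exposure period of its own.
- **Exposure period.** It "will be assumed to last 180 days after drug administration/prescription/dispensation", cut at the end of follow-up.
- **Continuous use.** It applies "if no gap longer than 60 days occurs between the end date of the first inebilizumab exposure period and the beginning of the third".
- **Temporary discontinuation.** It requires "gaps between inebilizumab exposure periods longer than 60 days but with a subsequent inebilizumab administration/prescription/dispensation during the follow-up".
- **Permanent discontinuation.** It applies "if no subsequent inebilizumab treatment is registered during the follow-up after the end date of the first inebilizumab exposure period".
- **Switching.** "Switchers will be a subgroup of patients who discontinue inebilizumab (temporarily or permanently) during the follow-up". The patient must also have a Table 9 drug after the exposure period ends.
- **Add-on.** A Table 9 or Table 10 drug counts if it is given, prescribed or dispensed "during any of inebilizumab exposure period". Corticosteroid pre-medication is excluded.

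Section 6.7.2.2 refers back to these definitions for the proportions of patients with each pattern. It measures time to add-on from the index date to the earliest recorded start of an add-on drug.

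**The concern.** The 60-day allowance is applied to one definition and not to the one beside it. For the continuous-use label, days between the end of the first exposure period and a third infusion up to 60 days later are treated as uninterrupted. For add-on, the same days are treated as unexposed. Switching does not pick them up, because a continuous user is not a discontinuer.

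Add-on use is a named result of objective 2, and follow-up is only 12 months. A drug with a single record, or with widely spaced records, can be lost from that result if the record falls in the gap. The loss can occur only in patients whose third infusion is later than day 181, so it is tied to infusion timing and is not random.

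**Working it through.** The plan states no figure for this, so there is none to reproduce. The check applies the rules literally.

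**Inputs (section 6.3.3).** Exposure length 180 days; tolerated gap up to 60 days; follow-up 12 months, taken as 365 days. Let day 0 be the index date and d3 the day of the third infusion. Day 180 is taken as the last exposed day of the first period, and the day of the third infusion as exposed.

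**Step 1: latest infusion still classed as continuous.** 180 + 60 = day 240.

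**Step 2: unclassified days.** For a continuous user, days 181 to d3 − 1 lie in no exposure period. Their number is d3 − 181.

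| Third infusion (d3) | Gap, d3 − 180 | Unclassified days, d3 − 181 | Share of 365 days |
|---|---|---|---|
| 181–184 (6 calendar months) | 1–4 | 0–3 | under 1% |
| 195 | 15 | 14 | 3.8% |
| 210 | 30 | 29 | 7.9% |
| 240 | 60 | 59 | 16.2% |

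**Step 3: how a record in that window is classified.** Take a Table 9 drug recorded once, on day 210, with the third infusion on day 240.

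- Add-on: no. Day 210 is after day 180 and before day 240.
- Temporary discontinuation: no. The gap is 60 days, not longer.
- Permanent discontinuation: no. A later infusion is recorded.
- Switch: no. The patient has not discontinued.

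The record is in no category.

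**Step 4: drugs recorded again.** A drug recorded again on or after d3, within follow-up, meets the add-on rule through that later record. Whether a later record exists depends on the interval between records, which the protocol does not give. With d3 = 240, starts on days 181 to 239 and assumed intervals:

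| Assumed interval | Start days with no later record by day 365 | Delay if the later record sets the date |
|---|---|---|
| 28 days | 0 of 59 | 28–84 days |
| 30 days | 0 of 59 | 30–60 days |
| 90 days | 0 of 59 | 90 days |
| 180 days | 54 of 59 | 180 days for the other 5 |

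In the last row a later record needs s + 180 ≤ 365, so only starts on days 181 to 185 qualify. The delays apply only if records outside exposure are ignored when the start is dated.

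**Step 5: possible effect on the proportion.** Assume 20% of patients have a one-off add-on start, uniform over the year.

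- 25% of patients infused at day 210, the rest on time: 0.20 × 0.25 × 29/365 = 0.4 percentage points lost.
- Every patient infused at day 240: 0.20 × 59/365 = 3.2 percentage points lost.
- For comparison, the 95% half-width for a proportion of 20% with the 400 patients of section 6.5 is 1.96 × √(0.20 × 0.80/400) = 3.9 percentage points.

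**Step 6: sensitivity to the week-2 infusion.** If it were counted, against the text, exposure would end at day 14 + 180 = 194, still 46 days before day 240.

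**The case against.** **The effect may be negligible.** An on-schedule infusion leaves at most 3 days, the large windows need a late infusion, and drugs recorded repeatedly are still counted. This stands. The less extreme illustration in the working loses 0.4 percentage points, well inside sampling error. It limits the size of the problem but does not supply the missing category.

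**This is SAP detail, or Figure 2 settles it.** Section 6.7.1 does leave full variable definitions to the SAP, and the panels of Figure 2 could not be seen for this review. But 6.3.3 already fixes the exposure length, the gap rule, the add-on window and who can be a switcher. A SAP that follows it reproduces the hole, and one that bridges the gap departs from the protocol text.

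**Add-on may properly mean overlap with assumed exposure.** That is a defensible definition. It sits badly with calling the same days continuous use, and it leaves the record unreported under any other heading.

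A reader might also infer more than the documents support:

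- *That time to add-on is overstated by up to 60 days.* The gap length is not a bound, as the assumed intervals show. If the earliest recorded start in section 6.7.2.2 is read to include the gap record, a patient who qualifies later keeps the right date. No effect on the planned median has been shown.
- *That treatment duration is wrong because tolerated gap days are left out.* Section 6.3.3 defines duration as a sum of exposed days. That measure can properly differ among continuous users, and changing it is a preference.
- *That the jump between day 240 and day 241 proves a defect.* With the infusion on day 241, the Table 9 record on day 210 becomes a switch. Any threshold produces such a jump, and one remains after the fix, from add-on to switch.
- *That late infusions prompt other treatment to cover the wait.* Nothing in the protocol says so.

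**Conclusion.** The point holds in limited form. For a continuous user with a third infusion after day 181 and up to day 240, section 6.3.3 has no category for a Table 9 or Table 10 drug whose only record falls between day 181 and the day before that infusion. The window is 0 to 3 days on schedule and at most 59 days. These counts follow from the stated rules, with day 180 taken as exposed; starting the window one day earlier adds one day.

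The number of patients affected cannot be calculated, because the protocol gives neither the distribution of third-infusion timing nor the frequency and spacing of other drug records. It may be small, and the documents do not show that objective 2 is materially distorted. The correction is still worth making, because following the plan exactly would drop valid records from a planned result and the remedy is cheap.

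**What to change.** Add one sentence to section 6.3.3 and carry it into the SAP. For patients who meet the continuous-use rule, the tolerated gap up to the next infusion counts as part of the exposure period when add-on use and time to add-on are derived. The date of the gap record is the start date, and the existing exclusion of corticosteroid pre-medication still applies.

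Leave treatment duration, the 60-day rule and the continuous and discontinued classes unchanged. The unclassified days between the two exposure periods of a continuous user then fall from as many as 59 to 0.

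The cost is a text edit and a small programming change, with no new data. The one downside is that a drug recorded after the assumed 180 days, in a patient with a late third infusion, will be labelled add-on. A footnote giving the number of such records would make this visible, subject to the small-number masking rules in section 6.7.1.

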4 RATIONALE AND BACKGROUND

4.1 Background

Neuromyelitis optica spectrum disorder (NMOSD; also known as Devic's syndrome and previously known as neuromyelitis optica [NMO]) is a rare, chronic, autoimmune, inflammatory disorder of the central nervous system, characterized by attacks of optic neuritis and longitudinally extensive transverse myelitis and, less frequently, affecting the brain and brainstem (1). Commonly reported symptoms include ocular pain, unilateral or bilateral loss of visual acuity that can lead to blindness, loss of sensation, weakness (including paraplegia), bladder and bowel dysfunction, paroxysmal tonic spasms of the trunk and limbs, and Lhermitte's phenomenon (1). Up to 90% of patients with NMOSD have recurring episodes of optic neuritis and/or myelitis rather than following a monophasic course (2). Attacks can be severe and result in blindness, paralysis, and even death due to neurogenic respiratory failure (3). An important paraclinical feature of NMOSD seen in 80% patients and used to help differentiate the condition from multiple sclerosis (MS) is the presence of serum autoantibodies against aquaporin-4 (AQP4) (i.e., AQP4-immunoglobulin [Ig]G or NMO-IgG) (4).

Worldwide, incidence rates of adult NMOSD are reportedly between 0.04-0.73/100,000 person-years (5), while the prevalence of NMOSD in adults is approximately 0.5-4/100,000 and may be up to 10/100,000 in certain racial groups (6). NMOSD can occur at any age, and disproportionately affects females (70%-90%), with a mean age of onset of approximately 40 years (6).

Treatment of NMOSD comprises 2 main goals: recovery from acute attacks and prevention of future attacks (relapse) as well as prevention of sequelae.

Recently, inebilizumab, an anti-CD19 B-cell depleting antibody, was approved for the treatment of NMOSD in AQP4-IgG seropositive patients in the US, Japan, and South Korea, and in November 2021 the Committee for Medicinal Products for Human Use of the European Medicines Agency (EMA) also recommended approval for the same patient population. The current recommended initial dose is 300 mg intravenous (IV) infusion followed 2 weeks later by a second 300 mg IV infusion. The recommended maintenance dose is a single 300 mg IV infusion every 6 months thereafter, starting 6 months from the first infusion (7).

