6.5 Study Size

This is a descriptive study that will identify and characterize the patients who are treated with inebilizumab. There is no *a priori* hypothesis testing and no prespecified requirement of sample sizes. The final study size will be determined by the length of study period and uptake of inebilizumab in the countries and population covered in the data sources. In order to comply with pharmacovigilance reporting commitments, multiple data extractions are planned for EU countries. Slow uptake may impact on the ability to meet the study objectives; in this instance the feasibility of study completion within the proposed time frame and need for further data extractions, should be open to re-evaluation.

For this observational study, the interpretation of results focuses on the precision of estimands (proportions). [Table 3](#) presents the sample sizes across a range of expected incidences (of patient characteristics or AESI) and levels of precision. The sample sizes are derived assuming a normal approximation for the 95% confidence intervals (CI). Thus, in this study a pooled cohort of 400 patients across data sources would enable a patient characteristic (or AESI) with an assumed incidence of 1% to be estimated with a precision of +/- 1%, and for a patient characteristic (or AESI) with an assumed incidence of 4% to be estimated with a precision of +/- 2%.

Table 3 Sample Sizes of Patients Required to Estimate the Expected (True) Cumulative Incidence of a Patient Characteristic or AESI With 95% Confidence Intervals of Different Precisions (0.2% to 5%)

Estimated Incidence (%)	Precision 0.20%	Precision 0.50%	Precision 1%	Precision 2%	Precision 3%
0.30	2 872	-	-	-	-
0.40	3 826	-	-	-	-
0.50	4 778	764	-	-	-
0.70	6 675	1 068	-	-	-
0.80	7 621	1 219	-	-	-
1.00	9 508	1 521	380	-	-
2.00	18 823	3 012	753	188	-
3.00	27 947	4 471	1 118	279	124
4.00	36 878	5 900	1 475	369	164
5.00	45 617	7 299	1 825	456	203

AESI, adverse events of special interest

Feasibility – Patient estimates

Data sources and study countries were selected following a high-level feasibility assessment. It addressed the appropriateness of data sources for completion of this study regarding the ability to identify the target population and the presence of some variables of interest (such as results for AQP4 testing).

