6.7.2.2 Objective 2: Treatment patterns of inebilizumab

The number and proportion of patients in the overall study population receiving the drug, and by dose stratification, (below or above the recommended dose in the product characteristics [300 mg/IV infusion]) will be reported at each of the first, second, and third infusion. Additionally, the number and proportion of patients who change dose between the individual infusions as well as the time (in days) between the first and each subsequent treatment (regardless of dose) will be reported.

Inebilizumab treatment patterns, as described below, will be assessed in the period of 12 months from index date and only patients with a complete 12-month follow-up, regardless of inebilizumab discontinuation, will be considered.

The number and proportion of patients who experience the following treatment pattern related events will be reported separately for each of the events: continuous and discontinuous treatment, switching, use of add-on therapies, according to what is defined in [section 6.3.3](#). For all the events, the denominator consists of all patients exposed to inebilizumab and followed for the full 12-month period.

The median time to switching and the median time to use of add-on drugs will be described in the subgroups of switchers and patients using add-on therapies (as defined in [section 6.3.3](#)), respectively. For the subgroup of switchers (as defined in [section 6.3.3](#)), the time to switch will be calculated as the time from the index date until the first recorded start date of another NMOSD maintenance drug. For the subgroup of patients using add-on therapies (as defined in [section 6.3.3](#)), the time to add-on drug use will be calculated as the time from the index date until the first recorded start date of an add-on drug.

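### Section 6.3.3: a third infusion on or before day 180, with none later in follow-up, makes a patient both a continuous user and permanently discontinued

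*Protocol*

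**What the plan says.** Section 4.1 gives the schedule: two initial infusions two weeks apart, then "The recommended maintenance dose is a single 300 mg IV infusion every 6 months thereafter, starting 6 months from the first infusion". Section 6.3.3 expects three infusions in the 12-month follow-up and bases the treatment patterns on the first and third.

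The rules in section 6.3.3 are:
- **Exposure period:** it "will be assumed to last 180 days after drug administration/prescription/dispensation". Its end date is brought forward only by the end of follow-up, not by an earlier next infusion.
- **Continuous use** applies "if no gap longer than 60 days occurs between the end date of the first inebilizumab exposure period and the beginning of the third".
- **Temporary discontinuation:** a gap of more than 60 days, with a later infusion in follow-up.
- **Permanent discontinuation:** "if no subsequent inebilizumab treatment is registered during the follow-up after the end date of the first inebilizumab exposure period".
- **Switchers:** "Switchers will be a subgroup of patients who discontinue inebilizumab (temporarily or permanently) during the follow-up" and who receive another maintenance drug after the end of exposure.

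Section 6.7.2.2 reports each pattern as a number and proportion: "For all the events, the denominator consists of all patients exposed to inebilizumab and followed for the full 12-month period". It also says that "the time (in days) between the first and each subsequent treatment (regardless of dose) will be reported".

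**The concern.** Continuous use and permanent discontinuation are presented as counterparts; the abstract speaks of patients who continue and who discontinue, respectively. For a patient infused early they are not exclusive. Continuous use looks at the size of the gap, which is zero or negative when the third infusion comes early. Permanent discontinuation asks whether anything is recorded after day 180, and an early third infusion is not. The text gives neither class precedence.

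Discontinuation frequency is a named part of Objective 2. If both rules are applied, the class proportions can exceed 100%. If permanent discontinuation is applied first, a patient who received the month-6 dose slightly early is reported as having stopped. The error runs one way: it adds to discontinuation.

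**Working it through.** **Inputs (section 6.3.3).** The first exposure period ends on day 180, the gap limit is 60 days, and follow-up is 12 months, taken as 365 days. Let t be the day of the third infusion, with no later infusion unless stated.

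**Rules as formulas.**
- Gap = t − 180.
- Continuous: gap ≤ 60, so t ≤ 240, with no lower limit.
- Temporary: gap > 60 with t in follow-up, so t = 241 to 365.
- Permanent: no infusion on days 181 to 365.

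| Third infusion (day) | Gap (days) | Continuous | Temporary | Permanent |
|---|---|---|---|---|
| 168 | −12 | yes | no | yes |
| 175 | −5 | yes | no | yes |
| 180 | 0 | yes | no | yes |
| 181 | 1 | yes | no | no |
| 184 | 4 | yes | no | no |
| 240 | 60 | yes | no | no |
| 241 | 61 | no | yes | no |
| 168, fourth on day 350 | −12 | yes | no | no |

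Every third-infusion day from 15 to 180 falls in both classes (to 179 if day 180 itself counts as after the end date). Days 181-240 are continuous only and days 241-365 temporary only.

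**Distance from the label date.** Six calendar months is 181 to 184 days. An infusion on the label date misses the overlap by 181 − 180 = 1 to 184 − 180 = 4 days.

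**Role of a fourth infusion.** Take a third infusion on day 175.
- If the fourth is timed six months from the third, it falls on day 175 + 181 = 356 to 175 + 184 = 359. That is inside follow-up, and the overlap disappears.
- If the fourth is timed from index, it is due at month 12, which averages 365.2 days and so lies on the boundary of follow-up. It can easily be missed, and the overlap then stands.

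The rule also separates like patients. Of two patients who both stop after the third infusion, one infused on day 179 is in both classes, while one infused on day 182 is continuous only.

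**Switchers.** With a third infusion on day 175, that exposure period runs to 175 + 180 = day 355. Suppose another maintenance drug starts on day 200. If the end date meant is that of the first period (day 180), this is a switch. If it is that of the latest period (day 355), the drug falls within exposure and is an add-on. On the second reading, a third infusion on days 170-180 leaves only about 365 − 350 = 15 down to 365 − 360 = 5 days in which a drug could count as a switch.

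**Size: illustration only.** The protocol gives no distribution of infusion dates. Assume normal scatter, so that P(t ≤ 180) = Φ((180.5 − centre)/SD):
- Centre 182.6: 0.27, 0.38, 0.44 for SD 3.5, 7, 14.
- Centre 190: 0.003, 0.087, 0.249, 0.326 for SD 3.5, 7, 14, 21.

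Requiring also no fourth infusion by day 365 (simulated in whole days):
- Centre 182.6: 3-9% if the fourth dose is timed from the third, 13-22% if timed from index.
- Centre 190: 0.3-12% or 0.3-21%.

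These shares are for patients still on treatment. The range runs from negligible to large, so it does not fix a size.

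**The case against.** The strongest reply has four parts.

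1. **The intent is readable.** Permanent discontinuation probably means no third infusion, and Figure 2, which the text cites for these definitions, may show that. The figure is not available here, so this point rests on the text. Even if the figure is clear, the sentence that defines the class says something else.
2. **The SAP will settle it.** Section 6.7.1 commits to one global SAP with full variable definitions. A reader might infer that the six data sources could each apply the rules in a different order; that commitment does not support the inference. However, the protocol does not defer this rule. It states one, and a SAP that follows it faithfully reproduces the overlap.
3. **The problem is visible.** Infusion intervals are reported under section 6.7.2.2, so affected patients could be re-tabulated. That makes the error detectable but does not correct the published proportions.
4. **The study is descriptive.** No hypothesis test is at risk. This limits the severity, but discontinuation frequency is itself an Objective 2 result.

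Three stronger readings should be set aside. Patients infused on the label date are not misclassified: days 181-184 are continuous only. A large spill into the switching proportion does not follow either, because it depends on which end date is meant. Nor can the effect be sized against "a pooled cohort of 400 patients across data sources" (section 6.5), since treatment patterns use only patients with complete 12-month follow-up, and section 6.9 warns that this group may be small.

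**Conclusion.** The point holds on the wording of section 6.3.3. A third infusion on or before day 180, at least 1-4 days before the label date, with none later in follow-up, satisfies both continuous use and permanent discontinuation. Objective 2 can then count a patient who received the maintenance dose as having stopped, which inflates discontinuation, or report proportions above 100% in total.

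The share affected cannot be derived from the protocol. It depends on how infusion dates scatter and on whether the fourth dose is timed from the third or from index, and neither is given. The conclusion assumes that Figure 2 does not override the text and that 12 months is 365 days. It is a wording error worth correcting before the rules are programmed.

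**What to change.** In section 6.3.3:
- Treat the index infusion, and any infusion within a short stated window after it (for example 30 days), as the initial course. This also covers a week-2 dose that is absent or shares a dispensing record.
- Define exclusive classes by the first infusion after that course: by day 240, including before day 181, is continuous use; from day 241 to the end of follow-up is temporary discontinuation; none by the end of follow-up is permanent discontinuation.
- Count a switch only when the other drug starts after the end of the most recent inebilizumab exposure period. Earlier starts count as add-on.
- State that stopping after the month-6 infusion cannot be recognised within 12 months: an infusion on day 181-184 carries exposure to day 361-364.

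Use the same classes in section 6.7.2.2.

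One case remains a matter of judgement. An infusion far ahead of schedule, say on day 60 with none later, would be continuous although its exposure ends on day 60 + 180 = 240, which is 125 days before follow-up ends. The infusion intervals already planned in section 6.7.2.2 will show whether such cases occur.

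The cost is wording in sections 6.3.3 and 6.7.2.2. No new data, longer follow-up or extra tables are needed.
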